8.1 Primary longitudinal analysis (HM-PRO)

- **Primary modelling approach:** linear mixed-effects models (LMM) for repeated measures of HM-PRO scores to evaluate within-hospital trajectories and between-group differences. The base model will include:
 - Fixed effects for **timepoint (categorical: T1, T2, T3, T4, T5), treatment group**, and the **group × time** interaction (to test for differential trajectories).
 - A random intercept for participant to account for within-subject correlation; random slope for time will be considered if supported by data and model fit.
 - Prespecified covariates: baseline HM-PRO score (if modelling discharge score via ANCOVA alternatively), age, sex, disease type, disease status, line of therapy, major comorbidity index, and site (as fixed effect or as random effect in a hierarchical model).

- Parameter of interest: the group \times time interaction contrasts (e.g., difference in mean change from baseline to discharge between groups). Report estimated marginal means (least-squares means), differences, 95% CIs and p-values.
- **Model diagnostics:** check residuals for normality and heteroscedasticity, influence diagnostics, and perform sensitivity analyses using robust standard errors if necessary. If severe non-normality persists, consider transformation or a generalized linear mixed model (GLMM) or rank-based mixed model.

Repeated measures ANOVA

- As a supportive analysis (or when assumptions are met and complete data are available), repeated-measures ANOVA (with Greenhouse-Geisser correction if sphericity violated) may be used to summarize overall time and group effects. Primary inference will rely on mixed models which better accommodate missingness and unequal intervals.

Between-group comparisons & ANCOVA

- For the primary endpoint specified as change from baseline to discharge, an **ANCOVA** model will be used (discharge HM-PRO as outcome, baseline HM-PRO as covariate, plus the same prespecified covariates). This produces an adjusted estimate of the between-group difference in mean change.
- Unadjusted two-sample t-tests (or nonparametric Wilcoxon tests) will be presented for transparency.

Subgroup analyses

- Exploratory subgroup analyses will be performed for: disease type (AML vs lymphoma vs myeloma), disease status (remission vs progression), age strata, and treatment line. Each subgroup analysis will include a formal **interaction test** (group \times subgroup) within the primary model rather than separate stratified unadjusted tests. Subgroup results are exploratory and interpreted cautiously.

Correlation / association between adverse events and PROs

- **Correlation analyses:** relationship between AE burden (grade or counts) and HM-PRO scores will be examined using Spearman's rank correlation (for ordinal AE grades) or Pearson correlation if assumptions hold.
- **Regression analyses:** to examine whether specific AEs (e.g., CRS, ICANS, mucositis, infections, GvHD) are associated with concurrent or subsequent HM-PRO scores, include AE indicators or graded severity as fixed effects in the mixed model (time-varying covariates). Logistic or Poisson regression (or negative binomial) may be used where appropriate (e.g., modelling probability of clinically meaningful deterioration, or AE counts). Report adjusted effect estimates (e.g., mean differences, odds ratios, incidence rate ratios) with 95% CIs.

- Pre-specify temporal directionality in the SAP (e.g., whether AEs occurring before an HM-PRO assessment are considered predictors).

Handling of missing data

- **Item-level HM-PRO missingness:** per the HM-PRO scoring manual, **missing item responses will not be substituted**; scores will be calculated according to the instrument's guidance.
- **Missing assessments / visit-level missingness:** for missing entire HM-PRO assessments (e.g., missed T2, T3, T4 or T5), the primary approach will be **multiple imputation by chained equations (MICE)** under a missing at random (MAR) assumption. Imputation models will include baseline and post-baseline HM-PRO items/scores, demographic and clinical covariates, laboratory markers, site, and indicators predictive of missingness. We will perform at least $m = 20$ imputations (or more if fraction of missing information is high) and combine estimates by Rubin's rules.
- **Sensitivity analyses:** compare results from: complete-case analysis, multiple imputation, and worst-case / tipping-point analyses to assess robustness to missing not at random (MNAR) mechanisms. The SAP will detail variables included in imputation models and diagnostics for imputation quality.

Multiplicity and inference

- Multiple secondary endpoints and subgroup tests are planned; these will be described as exploratory. Where formal control of family-wise error is desired for predefined secondary endpoints, procedures (e.g., Holm or Benjamini-Hochberg false discovery rate) will be specified in the SAP.

Additional analyses

- **Proportion with clinically meaningful deterioration:** compute proportion of participants with ≥ 6 -point worsening from baseline to discharge and compare groups using chi-square tests and logistic regression adjusted for covariates; report risk differences and adjusted odds ratios with 95% CIs.
- **Sensitivity for clustering:** if substantial between-site heterogeneity is present, use mixed models with random site intercepts or a generalized estimating equations (GEE) approach with robust SEs clustered by site.
- **Exploratory trajectories:** use latent class growth modelling or clustering of longitudinal profiles if warranted to identify common PRO trajectory phenotypes (reported descriptively).

Reporting

- All results will be reported according to STROBE guidance for observational studies and following best practices for PRO reporting (including instrument scoring details, number of missing items, and sensitivity analyses). Statistical code and de-identified

analytic datasets will be archived as per institutional policies and will be made available on reasonable request, consistent with GDPR and ethics approvals.

8.2. Sample Size:

The primary objective was to detect a between-group difference in HM-PRO between groups based on the difference in HM-PRO total score of $\Delta = 6$ points (the established Minimal Important Difference). Assuming a two-sided $\alpha = 0.05$ and 80% power, the required sample size per group was calculated using the two-sample t-test formula:

$$n = (2(z_{(1-\alpha/2)} + z_{(1-\beta)})^2 \sigma^2) / \Delta^2$$

Because the SD of HM-PRO change in our population is uncertain, we present results for a range of plausible SDs: for SD = 12 the required sample size is 63 per group (80% power); for SD = 15 it is 98 per group. If the primary analysis adjusts for baseline HM-PRO using ANCOVA and the correlation between baseline and outcome is r , the residual variance is approximately $\sigma^2 (1-r^2)$ and the required sample size is reduced accordingly (for example, with SD = 15 and $r=0.5$, $n \approx 74$ per group). We inflated the calculated sample size by 10% to allow for anticipated loss to follow-up (final target n per group = 81). All sample-size calculations were performed in R using power.t.test.

9. Methods

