- Difference in HM-PRO total and domain scores between allo-SCT and CAR-T groups at each time point (T1–T5)

Secondary Endpoints:

- Change in HM-PRO scores over time within each group
- Comparison of PROs by disease status and treatment line
- Frequency and severity of adverse events and correlation with PRO data

8. Statistical Analysis

- All analyses will be performed using two-sided tests with a nominal significance level of $\alpha = 0.05$ unless otherwise stated. Estimates will be reported with 95% confidence intervals.

Primary analysis population include all enrolled participants with at least one post-baseline HM-PRO assessment (intention-to-observe principle).

- Baseline demographic and clinical variables will be summarized by treatment group (allo-SCT vs CAR-T).

- **Continuous variables:** mean (SD) and median (IQR) as appropriate.
- **Categorical variables:** counts and percentages.
- Between-group baseline comparisons will be descriptive (t-tests/Wilcoxon tests or chi-square/Fisher exact tests) to display balance; inferential testing of baseline covariates is not the primary focus. A baseline table will be produced.

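### Read in the usual way, the primary mixed model's random intercept gives all five visits one SD and one correlation; if these differ by visit, its standard errors are wrong in either direction

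*Protocol*

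**What the plan says.** Section 7 of the Protocol defines the primary endpoint as "Difference in HM-PRO total and domain scores between allo-SCT and CAR-T groups at each time point", so Day 10 counts as much as discharge. Section 8.1 analyses this with a linear mixed model. The fixed effects include "timepoint (categorical: T1, T2, T3, T4, T5), treatment group" and their interaction. The within-patient part is "A random intercept for participant to account for within-subject correlation; random slope for time will be considered if supported by data and model fit". The parameter of interest is the set of group × time contrasts, with the "difference in mean change from baseline to discharge between groups" as the example.

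On which analysis decides, the section states: "Primary inference will rely on mixed models which better accommodate missingness and unequal intervals". Residuals are to be checked for heteroscedasticity, and the remedy is to "perform sensitivity analyses using robust standard errors if necessary". A Greenhouse-Geisser correction is planned, but only for the supportive repeated-measures ANOVA. Change from baseline to discharge is also analysed by ANCOVA, and unadjusted two-sample tests are reported. Missed assessments are multiply imputed and pooled by Rubin's rules.

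**The concern.** A random intercept with independent, equal-variance residuals imposes compound symmetry: one SD at every visit and one correlation for every pair of visits. Infusion to Day 3 is then treated as being as strongly correlated as admission to discharge, which may be up to three months apart. The section prefers mixed models partly because they cope with unequal intervals, yet this covariance ignores the intervals.

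With complete data and a saturated group × time mean (covariates left out), the estimated contrasts are the same under any covariance. Only their standard errors change. At stake are therefore the confidence intervals and p-values of primary results at single visits and for the change contrasts. The supportive ANOVA is protected against this kind of departure. The primary model is protected only by an optional slope, chosen from the data, and by robust standard errors that rank as a sensitivity analysis.

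**Working it through.** **Inputs from the Protocol.** 81 patients per group, five visits, two-sided α = 0.05, a difference of 6 points, SD 12 or 15, r = 0.5.

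**Sample size reproduced.** n = 2(1.960 + 0.842)²σ²/6². SD 12 gives 62.8, so 63. SD 15 gives 98.1 (stated as 98; 99 if rounded up). SD 15 with r = 0.5 gives 98.1 × 0.75 = 73.6, so 74. Then 73.6 × 1.10 = 80.9, so 81. This calculation concerns a single score and does not use the five-visit covariance.

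**Assumptions (the Protocol gives no figures by visit).**
- SDs for T1–T5 relative to admission: equal; 1/1/1.1/1.2/1.05; 1/1/1.2/1.4/1.1; 1/1/0.95/0.85/1; rising 1/1.05/1.1/1.15/1.2.
- Correlations by lag: constant 0.5; 0.60/0.57/0.53/0.50; 0.70/0.63/0.56/0.50; 0.80/0.70/0.60/0.50; AR(1) with 0.84.
- Slope coded 1–5, or in days as −7, 0, 3, 10, 25.

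**Method.** For a contrast c, true covariance Σ and best-fitting (Kullback–Leibler) model covariance V, the actual two-sided error is 2Φ(−1.96·√(c′Vc / c′Σc)). For the random-intercept model, V takes the average variance and the average covariance.

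**Day-10 difference, intercept only.** The ratio is pooled SD over true SD.
- +20%: √[(1 + 1 + 1.21 + 1.44 + 1.1025)/5] = 1.073; 1.073/1.2 = 0.894; error 8.0%.
- +40%: √[(1 + 1 + 1.44 + 1.96 + 1.21)/5] = 1.150; 1.150/1.4 = 0.821; error 10.7%.
- −15%: √[(1 + 1 + 0.9025 + 0.7225 + 1)/5] = 0.962; 0.962/0.85 = 1.13; error 2.7%.

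| Day-10 SD | Intercept only | With linear slope | Intercept + visit-specific residual variances |
|---|---|---|---|
| +20% | 8.0% | 7.4–8.9% | 6.0–6.8% |
| +40% | 10.7% | 9.6–11.3% | 6.7–8.1% |
| −15% | 2.7% | 2.7–3.5% | 3.6–4.0% |

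Ranges run over the five correlation patterns and, for the slope, both time codings. With equal SDs the intercept-only error is exactly 5.0% at every visit. With the steadily rising SD it is 6.0% at Day 10 (slope 5.3–6.7%) and 7.2% at discharge (slope 3.7–5.6%).

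**In points.** The 95% half-width is 1.96 × SD × √(2/81). With an admission SD of 15, the intercept model reports 5.0 where 5.5 is correct (+20%), 5.3 where 6.5 is correct (+40%), and 4.4 where 3.9 is correct (−15%).

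**Change contrasts, equal SDs.** Take correlations 0.70/0.63/0.56/0.50. The average is (4 × 0.70 + 3 × 0.63 + 2 × 0.56 + 0.50)/10 = 0.631.
- T1–T5: model variance 2(1 − 0.631) = 0.738, true variance 2(1 − 0.50) = 1.000, ratio √0.738 = 0.859, error 9.2%.
- T1–T4: 0.738 against 2(1 − 0.56) = 0.880, ratio 0.916, error 7.3%.

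Over the four fading patterns, the T1–T5 error is 6.8%, 9.2%, 12.9% and 14.0% with intercept only. With a slope it is 3.9–4.8%. The T1–T4 change is different: with the slope coded in days it stays at 7.3–10.3% for the three stronger fading patterns.

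**The proposed replacement.** An unstructured covariance has V = Σ in large samples, so the error is 5% for every contrast. Simulation with complete data (correlations 0.70/0.63/0.56/0.50, 4,000 replicates) gave a Day-10 error of 5.1% for both the unstructured model and the robust-SE fallback, under equal, +20%, +40% and −15% Day-10 SDs. With about 16% of Day-10 visits missing at random and imputed (m = 20, 2,000 replicates), both gave 4.7–4.9%, against 4.7/7.8/10.1/2.4% for the intercept model.

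**The case against.** The strongest objection is that the Protocol fixes only a random intercept. Equal, independent residuals are a software default, not stated text, and an SAP that is not at hand may name a residual structure. This stands in part. A reader might infer that the Protocol prescribes one SD and one correlation; it does not say so. But keeping the random intercept and adding visit-specific residual variances repairs the Day-10 error only partly, as the table shows. If the SAP names a fully unstructured residual covariance, the point is met and the random intercept becomes redundant.

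Second, the word linear does not appear. Time is categorical, and a random slope for it could mean one random effect per visit, which amounts to an unstructured covariance. That reading is possible, but it is not the ordinary one, and the slope is optional either way.

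Third, safeguards exist. Robust standard errors would correct the error, but they are ranked as a sensitivity analysis to be run if needed. The unadjusted two-sample tests do not pool SDs across visits, but they are given for transparency and are not the primary inference. The ANCOVA is sound for baseline to discharge, and Section 3.1 states the primary estimand as a difference in change. It does not cover T2–T4, which Section 7 makes primary.

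Fourth, the size rests on assumed patterns. This stands in full.

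**Conclusion.** The concern holds under the usual reading of Section 8.1: the primary standard errors are valid only if SDs and correlations are the same at all five visits. The direction of any error is unknown. In the illustrations the nominal 5% becomes 2.7% to 10.7% for the Day-10 difference, and 6.8% to 14.0% for the T1–T5 change when correlations fade and no slope is added.

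Three stronger readings are tempting and not supported. First, nothing in the Protocol shows that spread peaks or dips at Day 10, so the reported p-values cannot be said to be too small. Second, a slope is neither a general cure nor useless: it largely corrects the T1–T5 change under fading correlations, changes a Day-10 peak or dip little, and leaves the T1–T4 change uncorrected when coded in days. Third, the ANCOVA, the two-sample tests and the sample size are not affected.

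The figures assume 81 per group, no covariates and, for the analytic results, complete data. This should be changed before data are seen; it does not undermine the design.

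**What to change.** Keep categorical time × group. Replace the random intercept and optional slope by an unstructured within-patient covariance over T1–T5 (5 × 6/2 = 15 parameters, 162 patients) with a small-sample df correction. State the fallback in advance: if the model does not converge, use the random-intercept model with participant-clustered robust standard errors as the primary standard errors. Pool estimates and these standard errors over imputations by Rubin's rules with the small-sample df adjustment. If the random slope was meant as one random effect per categorical visit, say so and make it the primary structure rather than an option.

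The cost is a few lines of wording and a critical value of about 1.975 (160 df) instead of 1.960, or about half a power point. For the mixed-model T1–T5 change at SD 15, r = 0.5 and 74 per group, the SD of change is 15 × √(2 × 0.5) = 15 and the standard error is 15 × √(2/74) = 2.466. Then 6/2.466 = 2.433, and power goes from Φ(2.433 − 1.960) = 68.2% to Φ(2.433 − 1.975) = 67.7%. The small convergence risk is covered by the fallback.

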The Hematological Malignancy Patient-Reported Outcome (HM-PRO) is a validated instrument specifically developed to assess health-related quality of life (HRQoL) and symptom burden in patients with HM [16–20]. It consists of two parts: Part A evaluates the impact of disease and treatment on HRQoL, and Part B assesses the severity of symptoms. HM-PRO has undergone rigorous psychometric validation, demonstrating strong content validity, construct validity, reliability, and sensitivity to change across a broad spectrum of hematologic malignancies [16–18]. Its disease-specific design makes it particularly suitable for capturing the dynamic and treatment-specific symptom profiles observed in allo-SCT and CAR-T recipients.

Given the distinct toxicity and recovery profiles of allo-SCT and CAR-T therapy, a prospective observational study is warranted to compare short-term PRO trajectories between these two patient groups during the inpatient treatment course. Observational methodology is appropriate, as treatment allocation is determined by clinical indication rather than

randomization, and such a design enables the capture of real-world patient experiences in a non-interventional setting [21,22]. By employing the HM-PRO to collect PRO data at baseline, throughout hospitalization, and at discharge, this study will generate high-resolution, real-world evidence on patient experiences that are currently underrepresented in the literature. These findings will help inform supportive care strategies, improve patient-centered decision-making, and contribute to comparative effectiveness research in advanced cellular therapies.

2. Study Objectives

Primary Objective:

- To assess and compare short-term patient-reported outcomes [PROs (symptom burden and QoL impact)] between patients receiving allo-SCT and CAR-T therapy using the HM PRO from admission to hospital discharge.

Secondary Objectives:

- To describe PRO trajectories during hospitalization.
- To assess differences in PROs based on:
 - Treatment modality (allo-SCT vs CAR-T)
 - Disease type (e.g., AML, lymphoma, myeloma)
 - Disease status (remission vs progression)
 - Treatment line (first-line vs multiple lines)
- To validate the use of the HM-PRO in the context of inpatient care for advanced therapies.

3. Study Design

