3.1. Overview

Prospective, multicenter, observational cohort study comparing short-term PROs measured with the HM-PRO between two exposure groups: patients undergoing allogeneic stem cell transplantation (allo-SCT) and patients receiving CAR-T cell therapy. Patients will be enrolled at hospital admission for the index inpatient procedure and followed through the inpatient stay (admission → discharge). The study is non-randomized and designed to describe trajectories of symptoms and HRQoL and to estimate the between-group difference in deterioration of HM-PRO scores (primary estimand: mean difference in change score, CAR-T vs allo-SCT).

3.2 Setting:

Two tertiary care hospitals in Rome, Italy, with active allo-SCT and CAR-T in patient programs; multicenter to improve generalizability.

3.2 Duration:

1 year enrollment, participation from hospital admission to discharge (maximum 3 months).

4. Population

One hundred and sixty-two adults (≥ 18 years) with a hematologic malignancy admitted for either (a) allo-SCT (N=81) or (b) CAR-T cell therapy (N=81).

4.1 Inclusion Criteria:

- Age ≥ 18 years
- Diagnosed with a hematologic malignancy (e.g., leukemia, lymphoma, multiple myeloma)
- Undergoing either allogeneic SCT or CAR-T therapy
- Able and willing to provide written informed consent
- Sufficient Italian proficiency to complete the HM-PRO
- Signed informed consent

4.2 Exclusion Criteria:

- Cognitive or physical impairments that preclude the ability to complete questionnaires
- Estimated life expectancy < 7 days at the time of admission

5. Assessment Schedule

Patient-reported outcomes will be collected using the HM-PRO instrument at the following time points:

- T1: Hospital admission
- T2: Day of infusion (CAR-T or stem cell infusion)
- T3: Day 3 post-infusion
- T4: Day 10 post-infusion
- T5: Day of hospital discharge

6. Collected Variables

Demographics:

- Age, Gender, Education level, occupation, civil status

Clinical Variables:

- Comorbidities, Disease type, Disease status (remission/progression), Line of treatment

Laboratory:

- Full blood counts

Treatment:

- CAR-T or allo-SCT treatment details, including conditioning regimen and product specifics

Adverse Events:

- Documented using CTCAE criteria, including:
 - Mucositis, Infections, GvHD, CRS, ICANS

Patient-Reported Outcomes:

- HM-PRO (Impact Scale, Symptoms Scale)

7. Endpoints

Primary Endpoint:

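### Section 8.1 gives two primary-labelled analyses of change to discharge, and with covariates entered as listed the mixed-model contrast is not adjusted for them while the ANCOVA is

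*Protocol*

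**What the plan says.** Section 3.1 (Overview) describes a non-randomized study and states the target: "primary estimand: mean difference in change score, CAR-T vs allo-SCT". The background explains that "treatment allocation is determined by clinical indication rather than" randomization.

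Section 8.1 labels a linear mixed model as the primary modelling approach. Its fixed effects are categorical time (T1 to T5), group and group × time, with a random intercept and possibly a random slope. The covariates include "age, sex, disease type, disease status, line of therapy, major comorbidity index, and site". Baseline HM-PRO is listed only for the ANCOVA alternative. The parameter of interest is the set of group × time contrasts, with "difference in mean change from baseline to discharge between groups" as the example. The paragraph on repeated-measures ANOVA ends: "Primary inference will rely on mixed models which better accommodate missingness and unequal intervals".

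Under its own heading, section 8.1 then assigns the primary endpoint, when specified as change from baseline to discharge, to an ANCOVA with "discharge HM-PRO as outcome, baseline HM-PRO as covariate, plus the same prespecified covariates". It adds: "This produces an adjusted estimate of the between-group difference in mean change".

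Missing assessments are handled primarily by multiple imputation (MICE). Section 7 lists the primary endpoint differently, as group differences in score at each time point. Section 8.2 takes credit for the ANCOVA in its sample-size example of about 74 per group.

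**The concern.** In a comparison driven by clinical indication, disease type, disease status and line of therapy may differ between the groups, and adjustment is what makes the comparison interpretable. A reader who sees the covariate list in the base mixed model will assume that the group × time contrast has been adjusted for it. With the covariates entered as listed, it has not.

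If recovery by discharge depends on one of these factors, the mixed model attributes that dependence to CAR-T versus allo-SCT. The ANCOVA of the same change may then disagree with it for this reason alone. Since both carry a primary label, the choice between two discordant answers would be made with the data in view.

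**Working it through.** **The plan's own figures.** Section 8.2 uses n = 2(1.96 + 0.8416)² σ²/Δ² with Δ = 6.
- SD 12: 62.8, so 63 (stated 63).
- SD 15: 98.1 (stated 98; 99 if rounded up).
- SD 15, ANCOVA with r = 0.5: 98.1 × 0.75 = 73.6, so 74 (stated about 74).
- 74 × 1.10 = 81.4 (stated 81).

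All reproduce. The final 81 thus follows from the ANCOVA figure.

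**Why the covariates cancel.** With a free mean for every group and time point, a time-constant covariate x with coefficient γ changes the fitted mean of group g from ȳ(g,t) to ȳ(g,t) − γ·x̄(g). The subtracted term is the same at all five time points, so it drops out of T5 − T1 in each group and out of the difference between groups. This holds for any within-subject covariance when the data are complete, including each completed MICE data set. What remains is the raw difference in mean change.

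**Numerical check.** Assumptions: 73 per group (81 less 10%), SD of change 15, intraclass correlation 0.5, no true group effect, and one binary factor that affects T5 only, by 4 points. The factor is present in 51 of 73 allo-SCT and 22 of 73 CAR-T patients (about 70% versus 30%).

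| Mixed model | Group × T5 contrast | Variance |
|---|---|---|
| without the factor | −1.59 | 6.16 |
| factor as main effect (as listed) | −1.59 | 6.16 |
| factor × time added | 0.00 | 7.32 |

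By hand: 4 × 29/73 = 1.59, and 2 × 15²/73 = 6.16.

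A separate check used 81 per group and several covariates. The contrasts with and without main effects agreed to about 10⁻¹³, with the same standard error, under a random intercept and under an added random slope. With 10% or 25% of post-baseline visits missing and not imputed, the two differed by at most 0.17 or 0.34 points, and the assumed confounding remained.

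**What the covariates do achieve.** With a constant 4-point effect on level, and the factor in 36 of 73 allo-SCT and no CAR-T patients, the T5 level difference is −1.97 without the main effect and 0.00 with it. The endpoint in section 7 is therefore adjusted.

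**The ANCOVA.** In 4,000 simulations per setting over nine settings of this kind, its mean bias was at most 0.11 points and its rejection rate 4.5% to 5.8%.

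**Size of the shift.** Shift = (difference in share) × (effect on change). At 70% versus 30%, the normal-approximation false-positive rates use the whole-number counts above.

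| Assumed effect on change | Shift | False-positive rate |
|---|---|---|
| 2 points | 0.8 | 6% |
| 4 points | 1.6 | 10% |
| 6 points | 2.4 | 16% |

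**Precision cost of adjusting change.** For k binary factors, independent within group and each 70% versus 30%, the variance is multiplied by 1 + k × 0.4²/(4 × 0.21): 1.19 for k = 1 and 1.57 for k = 3. The mixed-model 95% half-width is 1.96√6.16 = 4.9 with none, 1.96√7.34 = 5.3 with one, and 1.96√9.69 = 6.1 with three.

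For the ANCOVA with r = 0.5, the starting variance is 0.75 × 6.16 = 4.62. If baseline scores are unrelated to group and factors, the half-widths are 1.96√4.62 = 4.2, 1.96√5.50 = 4.6 and 1.96√7.27 = 5.3.

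**The case against.** The strongest reply is that the protocol already has the right analysis. Section 8.1 ties change to discharge to the adjusted ANCOVA, and section 8.2 sizes the study with it. A reader might infer that primary inference rests on the unadjusted contrast alone. The documents do not support that: the sentence on primary inference closes the repeated-measures ANOVA paragraph and ranks mixed models against that method, not against ANCOVA. What remains is that the mixed model is also labelled primary, with the change contrast as its example parameter, and nothing says which of the two decides.

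A second reply is that entry as main effects is inferred, and that the SAP may add terms. The point is indeed conditional on covariates entered as listed. But the protocol itself sets out the base model and its parameter, and group × time is the only interaction with time it names there. The group × subgroup tests are exploratory and do not fill the gap.

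Third, a covariate with a constant effect on level drops out of change legitimately. Only an imbalanced factor that also affects recovery matters, and the documents quantify neither. This stands, and it limits what can be said about size. A reader might also infer that some disease-type or line cells are empty in one group; the protocol does not establish that, and the point does not need it.

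Fourth, covariate × time terms alone would not make the two analyses agree, because the mixed-model contrast does not condition on baseline. With a baseline slope of 0.5 and an assumed 6-point baseline difference between groups, the two differ by 0.5 × 6 = 3 points. This also stands, and it favours naming one primary analysis.

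**Conclusion.** The point holds in this form: section 8.1 has two primary-labelled analyses of change to discharge with different control of confounding. In one of them, the listed covariates do nothing for the primary estimand of section 3.1 if they are entered as written. That result is algebraic for complete or imputed data and nearly so otherwise.

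The size is not established. The 0.8 to 2.4 points at 70% versus 30% rest on assumed shares and effects, and lie below the 6-point minimal important difference. They show the route of bias, not its amount. The covariate list is not useless, since it adjusts differences in level, and the ANCOVA as written does adjust change. This should be settled before analysis because the correction is cheap; it does not show that the study's result will be wrong.

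**What to change.** In section 8.1, name the covariate-adjusted ANCOVA, fitted to the MICE data sets, as the single primary analysis of change from baseline to discharge. Keep the mixed model for trajectories and for level differences at each time point. This fits the role section 8.1 already gives the ANCOVA and the sample-size reasoning in section 8.2.

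If the mixed-model contrast is to stay primary, add covariate × time terms for all prespecified baseline covariates, at the least disease type, disease status, line of therapy and site. State then that the ANCOVA is supportive.

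The change is wording only and needs no new data collection. The cost is precision. Under the assumptions above, the mixed-model half-width rises from 4.9 to 5.3 points with one factor and to about 6.1 with three, and further if disease type has several levels or overlap between the groups is poor. An overlap-weighted sensitivity analysis is optional and not part of this point.

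### The exploratory test of whether age modifies the group difference uses age strata, although age is already a covariate in the same model; a continuous-age interaction would use the data better at no cost

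*Protocol*

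**What the plan says.** Protocol 8.1, under Subgroup analyses, names the variables to be examined as effect modifiers. They are disease type, followed by "disease status (remission vs progression), age strata, and treatment line". Each is to have a formal group-by-subgroup interaction test "within the primary model rather than separate stratified unadjusted tests". The same paragraph adds: "Subgroup results are exploratory and interpreted cautiously".

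The primary model, described earlier in 8.1, already adjusts for "age, sex, disease type, disease status, line of therapy" and other covariates. Age is on the list of collected variables in Section 6 ("Age, Gender, Education level, occupation, civil status") and again in 9.4, with no categories attached. The protocol gives neither the number of age strata nor their boundaries. It also does not say whether the age covariate enters the model as a continuous term.

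**The concern.** The other subgroup variables named are categories by nature or are defined as categories in the protocol. Age is not. When age is cut for an interaction test, the group difference is assumed constant within each stratum and to jump at its boundary. If modification is in fact gradual, the variation within strata is lost to the test. With more than two strata, the test also spends extra degrees of freedom.

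The protocol makes this choice itself. Boundaries written into a statistical analysis plan would carry the choice out; they would not recover the lost information.

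Interaction tests in a study sized for a main difference are weak to begin with. A smooth change in the group difference with age would be missed more often than it need be, on data the study already holds.

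**Working it through.** **The plan's own figure.** The protocol states no power or precision for the age test; its only sizing concerns the main difference. Inputs from Section 8 and 8.2: difference 6 points, SD 15, baseline–outcome correlation 0.5, two-sided 0.05, 80% power, 10% inflation.

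- n = 2(1.960 + 0.842)² × 15² / 6² = 98.1 per group
- with baseline adjustment: 98.1 × (1 − 0.5²) = 73.6
- inflated: 73.6 × 1.10 = 80.96, that is 81 per group and 162 in all

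This agrees with the protocol.

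**Assumptions for the age test (not in the documents).** Modification is linear in age. Age is roughly normal, with a uniform distribution as the alternative. Each patient contributes one outcome, as in the protocol's ANCOVA.

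**Information kept.** For a linear effect, strata keep the share of the variance of age that lies between strata: the sum of p × m², where p is the stratum's proportion and m its mean on a standardised scale. For a normal age and a median split, this is 2/π = 0.637. For a uniform age and k equal strata, it is 1 − 1/k².

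| Strata | Kept, normal | Lost, normal | Kept, uniform | Lost, uniform |
|---|---|---|---|---|
| 2 equal | 64% | 36% | 75% | 25% |
| 3 equal | 79% | 21% | 89% | 11% |
| 4 equal | 86% | 14% | 94% | 6% |
| 70/30 | 58% | 42% | – | – |
| 80/20 | 49% | 51% | – | – |

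**Power, starting from 80% on continuous age (normal age).** The standardised effect is 1.960 + 0.842 = 2.802, and its square is 7.85.

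- Median split: 2.802 × √0.637 − 1.960 = 0.276; power about 61%.
- 80/20 split: 2.802 × √0.490 − 1.960 ≈ 0; power about 50%.
- Three equal strata, 2 df: noncentrality 7.85 × 0.793 = 6.23; power about 60%.
- Four equal strata, 3 df: noncentrality 7.85 × 0.861 = 6.75; power about 57%.

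Adding strata recovers information, but the extra degrees of freedom use it up. Ordered stratum scores on 1 df would give about 70% (three strata) or 74% (four); the protocol does not specify them. With a uniform age the median split does better: 2.802 × √0.75 − 1.960 = 0.466, power about 68%.

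**Simulation check.** 4,000 simulated studies of 162 patients, normal age, residual SD 15 × √0.75 = 13.0: power 79% with continuous age and 59% with a median split.

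**In patients.** At a median split, 162 patients are worth 162 × 0.637 = 103 with continuous age. Restoring 80% power would take 162 / 0.637 = 254.

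**How far the 80% start is hypothetical.** At 162 patients and residual SD 13.0, 80% power needs the group difference to change by 2.802 × 13.0 × 2/√162 = 5.7 points per SD of age, nearly the whole 6-point minimal important difference. If continuous age had only 30% power, the standardised effect would be 1.960 − 0.524 = 1.436. After a median split it would be 1.436 × 0.798 = 1.146, with power about 21%: a drop of 9 points rather than 19.

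**The case against.** The strongest reply is that little depends on this test. Age is not among the secondary objectives (Section 2) or secondary endpoints (Section 7). It appears only in an analysis labelled exploratory, and the plan already uses interaction tests in an adjusted model rather than separate comparisons by subgroup. That is correct and sets the weight of the point, but it gives no reason to prefer the less efficient test on the same data.

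It can also be said that the size of the loss is not established. This stands too. The number of strata, the age distribution and the shape of any modification are all unstated, so only a range can be given, and the fall from 80% is an illustration. If modification is threshold-like and a boundary lies near the threshold, strata could do better than a linear term.

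Three stronger readings are tempting, and the document supports none of them.

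- A reader might infer that the boundaries will be chosen after seeing the data, so that the cut could drive the result. The protocol gives no boundaries, but these are commonly fixed in a statistical analysis plan, which is not at hand.
- A reader might infer that a large part of the information is lost whatever the strata. That fits two strata better than three or four.
- A reader might infer that stratifying spoils the adjustment for age generally. If the age covariate is continuous, only the modification of the group difference is coarsened; 8.1 does not state its form.

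**Conclusion.** The point holds as a minor, free improvement. The protocol tests effect modification by age in strata when age is available and already in the model. Under linear modification, two to four equal strata discard about 36% to 14% of the information if age is roughly normal and 25% to 6% if it is uniform; uneven two-way splits discard more (42% at 70/30 and 51% at 80/20, normal age). Starting from an illustrative 80%, power with two to four equal strata of a normal age, tested as categories, is about 57–61%. These figures rest on linearity and on an age distribution that the protocol does not give, and no interaction is powered in this study. The primary estimate, the sample size and the secondary endpoints are untouched.

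**What to change.** In 8.1, Subgroup analyses, replace age strata in the interaction test with a group-by-age interaction, age continuous, in the primary model. State that the age main effect is also continuous. Use a linear term for the main test. Fix any non-linear form in advance as a sensitivity analysis, for example a restricted cubic spline with its knots specified; do not add it only when the data suggest curvature. Report the between-group difference with its 95% confidence interval at two or three prespecified ages, so that the result is easy to read. Strata may remain for descriptive display.

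The cost is a change of wording: no new data, patients or procedures. The one downside is that a linear term is less sensitive to a threshold-like modification, which the prespecified spline partly covers.
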